7.3.1.2.4. Time to Response

Time to Response (TTR) is defined as the time from first dose to the first documented evidence of confirmed PR or better, among subjects who achieve a response (i.e., confirmed PR or better).

TTR will be summarized using Kaplan-Meier method. If data permits, median TTR, first and third quartiles and 95% CI, will be estimated using the Brookmeyer-Crowley method [Brookmeyer, 1982]. A listing of TTR time will also be provided. Summary of TTR will be based on Part 2 MM population; listing of TTR will be based on All Treated MM population.

7.3.1.2.5. Time to Best Response

Time to Response (TTBR) is defined as the time from first dose to the best confirmed response (PR or better), among subjects who achieve a response (i.e., confirmed PR or better).

TTBR will be summarized using Kaplan-Meier method. If data permits, median TTBR, first and third quartiles and 95% CI, will be estimated using the Brookmeyer-Crowley method [Brookmeyer, 1982]. A listing of TTBR time will also be provided. Summary of TTBR will be based on Part 2 MM population; listing of TTBR will be based on All Treated MM population.

7.3.1.2.6. Overall Survival

Overall survival (OS) is defined as the time from the date of first dose until death from any cause. For subjects who do not die, time of death will be censored at the date of last contact.

The protocol is amended to collect long-term survival data (i.e. up to 1 year after last subject completes or discontinues treatment). Subjects who are already completed the study will be contacted to request re-consent.

If all the patients (who were alive at the time of study completion) can be re-consented, OS landmark analysis may be performed at 9 and 12 months using Kaplan-Meier analysis as data permits. A listing of OS will also be provided. The OS landmark analysis will be based on Part 2 MM population; listing of OS will be based on All Treated MM population.

Otherwise, only descriptive analysis (number and % of deaths and lost to follow-up) will be performed.

7.3.1.3. Monoclonal Protein and Serum Free Light Chain

A waterfall plot showing the maximum percent reduction from baseline in Serum M-protein, or Urine M-protein, or difference between two types Serum FLC [Kappa light chain (Kappa LC) and Lambda light chain (Lambda LC)] for each subject will be produced using Part1 and Part 2 MM populations. Only the assessments from the start of treatment up to the start of new anti-cancer therapy will be considered. Only new systemic anti-cancer drugs taken are considered as anti-cancer therapy (radiotherapy and surgeries are not considered as systemic anti-cancer therapy for the purpose of this analysis). The maximum percent reduction will be plotted in the following hierarchical order:

- [1] Plot Serum M-protein maximum percent reduction from baseline if data is available;
- [2] If [1] is not feasible, plot Urine M-protein maximum percent reduction from baseline if data is available;
- [3] If both [1] and [2] are not feasible, plot maximum percent reduction from baseline for difference between two types of Serum FLC if data is available;

Difference between two types Serum FLC

The percent change from baseline for difference between two types of Serum FLC is defined as:

$$(\text{post-baseline difference} - \text{baseline difference}) / \text{baseline difference} * 100\%$$

To calculate the difference, the “involved” and “non-involved” light chains must be determined at first based on the ratio of non-missing values for Serum Kappa LC protein and Serum Lambda LC protein at baseline.

Detailed algorithm is provided as below:

- If the baseline ratio of (Kappa LC/Lambda LC) >1.65 , then Kappa LC is defined as involved FLC, and Lambda LC is defined as non-involved FLC. Then
 - Difference between involved and uninvolved = Kappa LC-Lambda LC
- If the baseline ratio of (kappa/lambda) <0.26 , then Lambda light chain is defined as involved FLC, and Kappa light chain is defined as non-involved FLC
 - Difference between involved and uninvolved = Lambda LC-Kappa LC
- If the baseline ratio of (Kappa LC/Lambda LC) ≤ 1.65 and ≥ 0.26 , then “involved” and “non-involved” FLC can not be determined (ratio is normal), and maximum percent reduction from baseline for difference between two types of Serum FLC won’t be available.

In addition, a scatter plot of free soluble BCMA at pre-dose (cycle 1) and maximum percent change from baseline in Serum M-protein, Urine M-protein or difference between two types Serum FLC will be provided following the hierarchical order specified above.

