- If a subject has neither progressed nor died nor started new anti-cancer therapy, then PFS will be censored at the date of the last adequate assessment defined as an assessment where the Investigator determined response is sCR, CR, VGPR, PR, MR or SD. The date of response will be used as the censoring date.

A summary of the assignments for progression and censoring dates for PFS are specified in Table 5.

Table 5 Assignments for Progression and Censoring Dates for PFS Analysis

Situation	Date of Event (Progression/Death) or Censoring	Outcome Event (Progression/Death) Or Censored
No (or inadequate) baseline tumor assessments ^[1] and the subject has not died (if the subject has died follow the rules for death indicted at the bottom of the table)	First dose date	Censored
No post-baseline assessments and the subject has not died (if the subject has died follow the rules for death indicted at the bottom of the table)	First dose date	Censored
Progression documented between scheduled visits	Date of assessment of progression ^[1]	Event
No progression (or death)	Date of last 'adequate' assessment of response ^[2]	Censored
New anticancer treatment started (prior to documented disease progression or death) ^[3] .	Date of last 'adequate' assessment of response ^[2] (on or prior to starting anti-cancer therapy)	Censored
Death before first PD assessment (or Death at baseline or prior to any adequate assessments)	Date of death	Event
Death between adequate assessment visits	Date of death	Event
Death or progression after an extended loss-to-follow-up time (two or more missed cycles + 7 day window) ^[4]	Date of last 'adequate' assessment of response ^[2] (prior to missed assessments)	Censored

1. In part 1, adequate baseline assessment is defined as at baseline, a patient has at least one of the following measurements: a. Serum M-protein or b. Urine M-protein or c. Serum FLC assay or d. Biopsy proven plasmacytoma (should be measured within 28 days of Screening Visit).

In part 2, adequate baseline assessment is defined as at baseline, a patient has at least one of the following measurements: a. Serum M-protein ≥ 0.5 g/dL (≥ 5 g/L) or b. Urine M-protein ≥ 200 mg/24h or c. Serum FLC assay: Involved FLC level ≥ 5 mg/dL (≥ 50 mg/L) and an abnormal serum free light chain ratio (< 0.26 or > 1.65) or d. Biopsy proven plasmacytoma (should be measured within 28 days of Screening Visit and no later than the first dose date).

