16.10.2.1.2. Clinical Response

Presence or absence of clinical response will be described using a conventional logistic regression model. Time to response will be explored using Kaplan Meier plots categorized by exposure measures.

PFS will be explored using Kaplan Meier plots categorized by exposure measures and occurrence of progression may also be described using a conventional logistic regression model.

Duration of response will be explored using Kaplan Meier plots categorized by exposure measures.

Best clinical response will be analyzed using an ordered logistic regression, with response categorized from 0 (progressive disease) to 6 (stringent complete response). Exposure will be treated as a categorical variable subdivided into quartiles and quintiles.

In the ordered logistic regression analyses, the use of categorical measures of exposure in lieu of continuous variables will allow for non-parametric descriptions of response functions.

Best clinical response as assessed by maximum reduction in M-protein or FLC will be analyzed by exposure (continuous and/or categorized by exposure measures).

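### For Part 2 MM, the maximum-reduction variable takes serum M-protein whenever a value exists, with no minimum baseline, so subjects who qualify by urine or FLC can be scored on a serum value below the plan's own 5 g/L level

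*SAP*

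**What the plan says.** SAP 7.3.1.3 sets a three-step hierarchy for the maximum percent reduction from baseline, to be shown in a waterfall plot "for each subject will be produced using Part1 and Part 2 MM populations".

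- Step 1: "Plot Serum M-protein maximum percent reduction from baseline if data is available".
- Step 2: "If [1] is not feasible, plot Urine M-protein maximum percent reduction from baseline if data is available".
- Step 3: "If both [1] and [2] are not feasible, plot maximum percent reduction from baseline for difference between two types of Serum FLC".

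Step 3 carries a baseline condition: the light-chain ratio must be below 0.26 or above 1.65, otherwise no FLC value is available. Steps 1 and 2 carry none.

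The same section applies the hierarchy to the scatter plot against soluble BCMA: "difference between two types Serum FLC will be provided following the hierarchical order specified above".

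Footnote 1 to Table 5 (7.3.1.2.1), repeated for Table 6 (7.3.1.2.2), treats baselines differently: "In part 2, adequate baseline assessment is defined as at baseline, a patient has at least one of the following measurements". The list opens with "a. Serum M-protein ≥ 0.5 g/dL (≥ 5 g/L) or b. Urine M-protein ≥ 200 mg/24h" and continues with involved FLC of at least 50 mg/L with an abnormal ratio, or a biopsy-proven plasmacytoma. For Part 1 the footnote names the same kinds of measurement but sets no levels.

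Section 16.10.2.1.2 also uses a maximum-reduction variable: "Best clinical response as assessed by maximum reduction in M-protein or FLC will be analyzed by exposure".

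**The concern.** The plan recognises Part 2 MM subjects whose only adequate baseline marker is urine M-protein or FLC. For such a subject, the marker that shows whether the disease is responding is the one that qualified. The hierarchy does not look at which marker that was. If a serum number exists, serum is used, however low its baseline.

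A percent change on a small denominator is unstable. The plotted value can then understate a response, show none, or point the opposite way from the qualifying marker. On Figure 12.0011 the bar can disagree with the best confirmed response printed on it. On Figure 12.0021 a point can sit at the wrong height. If MAXPRED follows the same hierarchy, the error also reaches the exposure-response analysis of maximum reduction.

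**Working it through.** The plan states no figure for this variable, so there is none to reproduce. The check sets the rules side by side and applies them to assumed subjects.

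**1. Can a Part 2 subject qualify with serum below 5 g/L?** Yes. Footnote 1 to Tables 5 and 6 needs only one criterion, and urine or FLC is enough.

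**2. Will such a subject usually have serum data?** Probably. The Part 2 MM schedule (16.2.3.1) lists the serum M-protein calculation at screening, at C2D1 and at the start of each later cycle. Section 16.6.3 converts non-detectable serum M-protein, urine M-protein and FLC results into numbers. Under its convention an assumed result of <0.5 g/dL, with one digit, becomes 0.5 - 0.1 = 0.4 g/dL (4 g/L). If every later result is also <0.5, the plotted change is (0.4 - 0.4)/0.4 = 0%, whatever the qualifying marker does.

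**3. How sensitive is the percentage to a low baseline?** A 1 g/L change as a percentage of baseline is 1/baseline × 100:

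| Serum baseline (g/L) | 1 | 2 | 3 | 4 | 5 | 20 | 30 |
|---|---|---|---|---|---|---|---|
| 1 g/L change | 100% | 50% | 33.3% | 25% | 20% | 5% | 3.3% |

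Every baseline below 5 g/L gives more than 20%.

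**4. What does the hierarchy plot?** The formula is (post - baseline)/baseline × 100. Section 7.3.1.3 gives it for the FLC difference; I use the same form for serum and urine. All subject values are assumed. Each post-baseline figure is the lowest value that marker reaches before new therapy, because the variable is a maximum reduction. FLC qualifiers are assumed to have urine below 200 mg/24h.

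| Assumed Part 2 subject | Serum (g/L) | Qualifying marker | As written | With baseline levels applied |
|---|---|---|---|---|
| FLC qualifier, responding | 2 to 1 | FLC difference 495 to 20 mg/L | -50.0% | (20 - 495)/495 = -96.0% |
| FLC qualifier, serum flat | 2 to 2 | FLC difference 495 to 20 mg/L | 0.0% | -96.0% |
| FLC qualifier, FLC rising | 2 to 1 | FLC difference 495 to 700 mg/L | -50.0% | (700 - 495)/495 = +41.4% |
| Urine qualifier, responding | 3 to 2 | Urine 800 to 60 mg/24h | -33.3% | (60 - 800)/800 = -92.5% |
| Urine qualifier, serum baseline zero | 0 | Urine 800 to 60 mg/24h | -92.5% | -92.5% |

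In the last row the serum percentage is undefined, so step 1 presumably fails and the two rules agree.

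**5. What would follow for RESPRATIO?** Sections 16.9.1 and 16.10.1 define it as max((100 + MAXPRED)/100, 0.001). In the third row this is 0.50 as written against 1.414 with the levels applied. This holds only if MAXPRED is derived by the 7.3.1.3 hierarchy.

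**The case against.** The strongest reply is that the hierarchy breaks no stated rule. The levels in Tables 5 and 6 define an adequate baseline assessment for PFS and TTP censoring. The plan does not label them measurable-disease thresholds there, and nothing says that they govern a waterfall plot. That is right. A reader might infer a direct contradiction; what the text supports is a rule that is badly fixed when set beside the plan's own notion of an adequate baseline.

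Other points on that side also stand:

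- A reader might extend the criticism to Part 1. The plan sets no levels there, so there is no mismatch with its own figures.
- It would be wrong to say that 7.3.1.3 ignores the baseline criteria altogether. Step 3 uses the same ratio limits; the serum, urine and involved-FLC levels are what is absent.
- One might infer that urine and FLC are reached only when serum is missing or zero. The trigger is feasibility, which is undefined, and a scheduled test does not prove that a quantified value is recorded for every light-chain subject.
- The low-baseline changes cannot be called assay noise. The document gives no M-protein assay precision or quantification limit.
- MAXPRED is taken from the response dataset without a stated derivation, and the exposure-response efficacy dataset carries RSPTYP, which identifies the marker.
- Figure 12.0011 prints the confirmed response and shades bars by test type, so some discordance would be visible. Figure 12.0021 has no fitted line.

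These points limit the reach of the concern. They do not repair the Part 2 rule. Showing the marker type or the response label tells the reader that a bar looks odd; it does not put the right marker on the plot.

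**Conclusion.** The concern holds for Part 2 MM. As written, 7.3.1.3 can score a urine- or FLC-qualifying subject on a serum baseline below 5 g/L, where a 1 g/L change exceeds 20% of baseline and the result can differ in size or sign from the qualifying marker (-50.0% against +41.4% in the assumed case).

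It affects the Part 2 waterfall (12.0011), the Part 2 soluble BCMA scatter (12.0021) and, only if they follow the same hierarchy, MAXPRED and RESPRATIO. All of this is exploratory. A reader might infer that the efficacy results are compromised. They are not: ORR, PFS, TTP and DOR rest on investigator-assessed response and progression and do not use this variable.

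The number of subjects affected cannot be derived from the document. It is the number in the Part 2 MM cohort (planned at up to 40) who qualify only by urine or FLC and also have a non-zero or imputed serum baseline below 5 g/L. The conclusion rests on reading step 1 literally, so that any recorded or imputed serum number counts as available data.

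**What to change.** In 7.3.1.3, for Part 2 MM, choose the marker by baseline level:

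1. Serum M-protein if baseline is at least 5 g/L.
2. Otherwise urine M-protein if baseline is at least 200 mg/24h.
3. Otherwise the FLC difference if involved FLC is at least 50 mg/L and the ratio is below 0.26 or above 1.65.
4. Otherwise no bar, with the subject listed as not plotted and the reason given.

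Define a step as not feasible when the baseline fails that level or no post-baseline value exists. Use the same choice for Figure 12.0021, MAXPRED and RSPTYP, and say so in the dataset specifications. State separately which rule applies in Part 1, where the plan sets no levels; carrying the Part 2 levels over would be a new decision and could remove bars.

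The cost is a few lines of text and a small programming change; the markers are already scheduled. The downside is that a few subjects without a qualifying marker, for example those with plasmacytoma only, will have no bar.

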7.3.1.4. Subgroup Analysis of ORR

A forest plot of ORR analysis will be provided for the following subgroups: Age, Sex, Ethnic Background, ISS Staging at Screening, Number of prior lines of therapy, Type of myeloma, Prior Daratumumab Treatment, Refractory to prior anti-cancer therapy, Cytogenetics Risk as defined in Section 5.2.1.

7.3.1.5. Population of Interest

The secondary efficacy analyses will be based on the “All Treated” population, unless otherwise specified (as in Section 4).

7.3.2. Strategy for Intercurrent (Post-Randomization) Events

Not applicable to this study.

7.3.3. Statistical Analyses / Methods

Details of the planned displays are provided in [Appendix 12](#): List of Data Displays and will be based on GSK data standards and statistical principles.

Unless otherwise specified, endpoints / variables defined in Section 7.2.1 will be summarised using descriptive statistics, graphically presented (where appropriate) and listed.

8. SAFETY ANALYSES

The safety analyses will be based on the “All Treated” population, unless otherwise specified.

8.1. Adverse Events Analyses

Adverse events analyses including the analysis of adverse events (AEs), Serious (SAEs) and other significant AEs will be based on GSK Core Data Standards. The details of the planned displays are provided in [Appendix 12: List of Data Displays](#).

An overview summary of AEs, including counts and percentages of subjects with any AE, AEs related to study treatment, AEs leading to permanent discontinuation of study treatment, AE leading to dose reductions, AEs leading to dose delays OR interruptions, SAEs, SAEs related to study treatment, fatal SAEs, and fatal SAEs related to study treatment will be produced.

A summary of non-serious AEs that occurred in strictly 5% of the subjects or above will be provided (no rounding for the percentage will be used in terms of 5% threshold, e.g., event with 4.9% incidence rate should not be included in this table). The summary will be displayed by SOC and PT.

The relationship between MedDRA SOC, PT, and Verbatim Text will be displayed.

Adverse events (AEs) will be graded according to the CTCAE, Version 4.0. Adverse events will be coded to the preferred term (PT) level using the Medical Dictionary for Regulatory Affairs (MedDRA dictionary).

A summary of number and percentage of subjects with any adverse events by maximum grade will be produced. AEs will be sorted by Preferred term (PT) in descending order of total incidence. The summary will use the following algorithms for counting the subject:

- **Preferred term row:** Subjects experiencing the same AE preferred term several times with different grades will only be counted once with the maximum grade.
- **Any event row:** Each subject with at least one adverse event will be counted only once at the maximum grade no matter how many events they have.

In addition, the frequency and percentage of AEs (all grades) will be summarized and displayed in two ways: 1) in descending order of total incidence by PT only and 2) in descending order of total incidence by System Organ Classes (SOC) and PT and Maximum Grade. In the SOC row, the number of subjects with multiple events under the same system organ class will be counted once.

A separate summary will be provided for study treatment-related AEs. A study treatment-related AE is defined as an AE for which the investigator classifies the relationship to study treatment as “Yes”. A worst-case scenario approach will be taken to handle missing relatedness data, i.e. the summary table will include events with the relationship to study

treatment as 'Yes' or missing. The summary table will be displayed in descending order of total incidence by SOC and PT and Maximum Grade.

All AEs will be listed. Additionally, a listing of subject IDs for each individual AE will be produced.

A listing of adverse events recorded as dose-limiting toxicities will be provided. Additionally, a summary of the number of patients experiencing DLT's in each cohort will be provided.

The summary of adverse event by SOC and PT and maximum grade, and AE by PT will also be produced for the following subgroups:

Prior anti-cancer therapy of interest:

- With prior Daratumumab Treatment and Refractory to Both Immunomodulators and Proteasome Inhibitors
- Without prior Daratumumab Treatment
- Refractory to Both Immunomodulators and Proteasome Inhibitors

8.2. Adverse Events of Interest Analyses

There are no pre-defined Adverse Events of Special Interest in the protocol, as it was a first time in human (FTIH) trial. During the course of the study, the analyses of the following adverse events of interest were included upon the safety review team (SRT) requests.

- Corneal events
- Thrombocytopenia
- Neutropenia
- Hematologic Toxicity
- Infusion-related Reactions as collected in the eCRF

For Corneal events, Thrombocytopenia, Neutropenia Hematologic Toxicity, a comprehensive list of MedDRA terms based on clinical review will be used to identify each type of event. Changes to the MedDRA dictionary may occur between the start of the study and the time of reporting and/or emerging data from on-going studies may highlight additional adverse events of interest, therefore the list of terms to be used for each event of interest and the specific events of interest will be based on the SRT agreements in place at the time of reporting. The details of the planned displays are provided in [Appendix 12: List of Data Displays](#).

Summaries of the number and percentage of subjects with these events will be provided for each type of events separately by preferred term and maximum grade. The time of

onset and duration of first occurrence of each type of events will be summarized using summary statistics mean, standard deviation, median, minimum value, and maximum. The number and percentage of subjects who have time of onset of first occurrence (1-21, 22-42, 43-63, >63 days) will be reported. The number and percentage of subjects who have duration of first occurrence (1-21, 22-42, >42 days) will be reported.

The summary of event characteristics will also be provided, including number of subjects with any event, number of events, number of subjects with any event that is serious, number of subjects with any event that is related to study treatment, number of occurrences (One, Two, Three or more), maximum grade and the action taken for the event. The percentage will be calculated in two ways, one with number of subjects with event as the denominator and the other with total number of subjects as the denominator. The worst-case approach will be applied at subject level for the maximum grade, i.e. a subject will only be counted once as the worst case from all the events experienced by the subject. For action taken to an event, subject will be counted once under each action, e.g. if a subject has an event leading to both study treatment discontinuation and dose reduction, the subject will be counted once under both actions.

